Participants will be withdrawn from the Infusion Substudy if they do not follow the instructions outlined in the protocol and informed consent form. Participants may also, at any time, choose to discontinue their participation from the Substudy.

S9. Outcome Measures (Infusion Substudy)

Primary Outcome Measure

Synthesis-secretion rates for omega-3 DHA with d5-LNA infusion, after 12-weeks of exposure to diets containing either 8 en% or 1 en% as omega-6 LA.

Human d5-LNA Infusion Model (adapted from [name] rodent model (64,65)).

The objective of this study is to quantify conversion rates of circulating unesterified plasma LNA into longer chain omega-3 fatty acids. It is assumed that most of this conversion will take place in the liver.

The idea is to infuse labeled d5-LNA, henceforth designated as LNA*, intravenously at a constant rate for up 8 hours, and to sample blood plasma (through a second intravenous catheter) periodically for measuring esterified and unesterified plasma concentrations of LNA* and omega-3 LCPUFAs (18:4n-3*, 20:4n-3*, 20:5n-3* (EPA), 22:6n-3* (DPA), 22:5n-3*, 24:6n-3*, and 22:6n-3* (DHA). Additionally, DEXA scan data from the primary protocol (11-AA-0028) will be used to estimate plasma volume V_{plasma} . Measurements also will be made of unesterified unlabeled LNA, DPA, EPA and DHA concentrations in plasma, to calculate actual conversion rates, as future studies may look at rates that may depend on these concentrations altered in disease or dietary states.

Initially, a constant infusion rate of approximately 2.2 umol/min will be established and infusion time will be 8 hours, for a total labeled infusion amount of 350 mg. Since the half-life of injected unesterified fatty acid is about 2 minutes in human plasma, a steady state concentration LNA* will be established within approximately 10 minutes after infusion is initiated. Duration and rate can be adjusted as necessary to properly determine the enrichment of the tracer and fatty acid kinetics.

Equations

Assuming linearity, the net rate of synthesis of a labeled omega-3 LCPUFA (e.g. DHA*) within secreted VLDLs or other lipoproteins from labeled LNA* is given as:

$$\frac{V_{plasma} dC_{DHA^*}}{dt} = \bar{k} C_{s-LNA^*}$$

The rate of disappearance of DHA* from plasma is given as:

$$\bar{k} C_{DHA^*}$$

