where concentrations C are nmol (or other units)/ml plasma, t is time after infusion has begun, k -appearance and k -disappearance are synthesis coefficients in units of time⁻¹, and V_{plasma} is plasma volume (estimated via DEXA scan). Because there is no isotope effect on enzyme kinetics, rate coefficients k -appearance and k -disappearance are valid for the unlabeled PUFAs as well.

The change in quantity of DHA* in plasma at any time after infusion begins equals:

$$\frac{V_{plasma} dC_{DHA^*}}{dt} = \bar{k} C_{s-LNA^*} - \bar{k} C_{DHA^*}$$

DHA can exist in two forms in plasma, esterified in lipoproteins and unesterified (after release from lipoproteins) and release of labeled unesterified fatty acid takes about 30 min to become evident in rat plasma after gavage (71). Because oxidative metabolism is 2.5 times faster in rats than in humans (69), it is expected that the delay may be up to 60-90 min. Additionally, during intravenous infusion of *LNA, esterified labeled n-3 PUFAs appear in plasma only after 30 min, and it is expected that in the present protocol they will also appear with a prolonged delay, between 60 and 90 min. In rat studies, the duration of intravenous infusion for 2 h has proven satisfactory (64, 65). For these reasons, we will start initially in humans with an infusion time of 8 hours, but may alter the duration depend on preliminary results.

However, the half-lives of LNA and DHA esterified in plasma lipoprotein (VLDL, LDL, HDL) in humans are 1 hour and 20 hours, respectively (70, 71). This means that after a delay in reaching steady-state rates of conversion of α -LNA to DHA and shorter chain n-3 fatty acid precursors into plasma lipoproteins, the initial slope of increased activity will essentially give the conversion coefficient k -

appearance. Any unesterified DHA* or other labeled unesterified omega-3 fatty acids that is released over time will have a half-life in plasma of about 2 minutes, and this will be taken into account as well.

In this study, we will use an infusion schedule to raise the concentration of d5-LNA as a step function, and will plot $V_{\text{plasma}} C_{\text{DHA}^*}$ against time. The initial slope relating the $V_{\text{plasma}} C_{\text{DHA}^*}$ against time after a delay will approximate the synthesis coefficient k^* for DHA*; similar coefficients can be obtained for the shorter chain labeled n-3 fatty acids.

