For more explicit analysis, as time proceeds, we will fit equation 4 to the data after inserting a time delay using a curve fitting procedure, to obtain \vec{k} for the different n-3 products. \vec{k} is the coefficient of conversion by whole body per given concentration of plasma LNA, in units of nmol/time, e.g. (nmol/ml, concentration) per unit time multiplied by ml (volume). This rate can be compared to our estimated rates of liver synthesis at the steady state, \vec{k} , in rats following the intravenous infusion of LNA* \vec{k} is the plasma unesterified concentration of LNA.

The concentration curves representing LNA* and DHA* should look like Figure 9:

[figure not shown]

Fig. 9. Graphical depiction of concentration curves for d5-LNA and DHA.

S10. Statistical Analyses (Infusion Substudy)

Overview

This Infusion Substudy first demonstrates feasibility for characterizing the hepatic synthesis-secretion rates of DHA from infused d5-LNA in humans, and then compares synthesis-secretion rates of omega-3 DHA in two diet groups that differ only in dietary omega-6 LA content.

Analysis of Data

Primary Aim 1: In the feasibility portion of this study we will define the dose, rate and duration of the d5-LNA infusion necessary to characterize synthesis-secretion rates of DHA from infused d5-LNA. Based on our previous experiences using this methodology in a rodent model, we anticipate that these data can be obtained from the first 4 infusion participants.

Primary Aim 2:

In the diet group comparison, we will compare synthesis-secretion rates for omega-3 DHA from d5-LNA in response to controlled dietary omega-6 LA lowering from 8 en% to 1 en%. The synthesis-secretion

rate of labeled serial concentration data for labeled DHA will be compared in the two diet groups using a t-test. A probability of 0.05 or lower will be considered significant.

The FADS genotype will be measured as part of the main protocol. This will allow us to assess whether the “low converter” FADS genotype is a modifying variable, or to rule it out as a confounder.

Estimation of Sample Size

We estimate that 4 to 12 individuals in each group are needed to provide adequate power (0.8) to test Primary Aim 2, as shown in Figure 10.

Estimation of Power and Sample Size

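### Infusion substudy, S9: neither stated unit for the conversion coefficient fits the printed kinetic equation, and the slope method omits division by the labelled LNA concentration

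*Combined protocol and SAP*

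**What the plan says.** S2 and S9 make the DHA synthesis-secretion rate the primary outcome of the infusion substudy. S9, under Equations, builds it in three steps. Synthesis of labelled DHA is a coefficient times the labelled LNA concentration. The loss is introduced with "The rate of disappearance of DHA* from plasma is given as", followed by a coefficient times the labelled DHA concentration. The two are then combined under "The change in quantity of DHA* in plasma at any time after infusion begins equals". With subscripts added here to tell the two coefficients apart, the combined equation is

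`V dC_DHA*/dt = k_a C_LNA* − k_d C_DHA*`

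where the asterisk marks labelled material and V is plasma volume.

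The definitions follow: "where concentrations C are nmol (or other units)/ml plasma, t is time after infusion has begun". Both coefficients "are synthesis coefficients in units of time" to the power minus one. In the curve-fitting paragraph, the fitted quantity "is the coefficient of conversion by whole body per given concentration of plasma LNA, in units of nmol/time". That paragraph spells the unit out as concentration per unit time multiplied by a volume, and its next sentence calls the quantity a rate and compares it with rat values.

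S9 also offers a simpler route: plot V times C_DHA* against time and take the initial slope, after a delay, as an approximation to the synthesis coefficient. It does not mention dividing by C_LNA*.

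In S10, Primary Aim 2 compares rates between diets by t-test. The sample-size paragraph says that rates and coefficients will both be compared, and does not say which is primary.

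**The concern.** A coefficient and a rate are different quantities. The coefficient describes how efficiently the body converts LNA. The rate is that efficiency multiplied by the LNA available. S9 gives the coefficient a unit that belongs to a rate, calls it a rate, and estimates it by a slope that is itself a rate.

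This matters because the slope depends on how much tracer is circulating. Two women with identical conversion efficiency but different labelled LNA concentrations would give different slopes. Concentrations can differ between participants at a given infusion rate. They would also shift if the infusion is changed, and S6 and S9 both provide for changing its rate and duration (S6 also its dose). An undivided slope carries all of this into the outcome that the t-test compares.

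**Working it through.** **Inputs, all from S9.** C is an amount per ml, taken as nmol/ml. V is a volume, taken in ml to match. S9 allows other amount units, but any amount per ml gives the same result.

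**Left side.** V dC/dt = ml × (nmol/ml) / time = nmol/time. This agrees with S9's description of it as a change in quantity.

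**Right side.** Each candidate unit for k, in the term as printed and with V added:

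| Unit of k | k × C, as printed | Balances? | V × k × C | Balances? |
|---|---|---|---|---|
| time⁻¹ (S9, both coefficients) | nmol/(ml·time) | no | nmol/time | yes |
| nmol/time (S9, conversion coefficient) | nmol²/(ml·time) | no | nmol²/time | no |
| ml/time (not in S9) | nmol/time | yes | nmol·ml/time | no |

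Two forms are consistent: the printed equation with both coefficients in ml/time, or both coefficients in time⁻¹ with V multiplying both right-hand terms. No form works with nmol/time. Only the conversion coefficient carries two units; the loss coefficient is given only in time⁻¹.

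**Initial slope.** Early on, C_DHA* is near zero and the loss term drops out, so

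- slope of V × C_DHA* = k_a × C_LNA*, in nmol/time;
- k_a = slope / C_LNA*, in (nmol/time)/(nmol/ml) = ml/time.

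The slope alone is therefore the rate of synthesis of labelled DHA. Fitting the balance equation, by contrast, returns k_a itself. The two routes in S9 estimate quantities that differ by the factor C_LNA*.

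**Actual rate.** k_a × unlabelled unesterified LNA concentration = (ml/time) × (nmol/ml) = nmol/time. The unit that S9 gives to the coefficient fits this rate or the labelled one.

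**Effect of not dividing.** For two participants with the same k_a and tracer concentrations in the ratio r, the slopes are also in the ratio r. Under the linearity that S9 assumes, halving the infusion rate halves C_LNA* and so halves the slope, with k_a unchanged. As a yardstick, the planned diet difference in Fig. 10 is 23.547 / 14.1 = 1.67, so a tracer ratio of 1.67 would produce the same contrast with no difference in conversion. The documents give no expected spread for C_LNA*, so this is a scale and not a forecast.

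**Sample size.** The difference in Fig. 10 is 23.547 − 14.1 = 9.447. Dividing by the three standard deviations:

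- 9.447 / 7.762 = 1.217: 12 per group, power 0.8130
- 9.447 / 6.4684 = 1.460: 9 per group, power 0.8284
- 9.447 / 3.7647 = 2.509: 4 per group, power 0.8386

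A two-sided t-test reproduces all three. They rest on standardized effects, so the units of the coefficient do not enter.

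**The case against.** The strongest defence is that this is a labelling slip in a damaged passage. Arrows over the symbols are lost in the available text, one symbol in the curve-fitting paragraph seems to stand for several things, and an equation 4 is cited although three expressions are visible. A sentence turning coefficient into rate may have been lost. The phrase about a given concentration of plasma LNA can also be read generously: nmol/time per nmol/ml is ml/time, the right unit. And S9 plans to measure labelled LNA, and unlabelled unesterified LNA for calculating actual conversion rates, so the analyst will have what is needed.

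Part of this stands: the data will exist, and the curve-fitting route can return a usable coefficient. But both units are stated in words, S9's own spelled-out unit is nmol/time, and the slope sentence is legible and omits the division.

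A reader might infer three stronger things that the documents do not support.

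- **A bias of about 10–13% in the appearance coefficient.** S9 states that "the half-lives of LNA and DHA esterified in plasma lipoprotein (VLDL, LDL, HDL) in humans are 1 hour and 20 hours" respectively. With L = ln 2 / 20 h, ignoring loss gives a mean slope of (1 − exp(−Lt))/(Lt) times the initial slope: 0.895 at 6.5 h and 0.873 at 8 h. Tying this to the units requires the half-life to be entered as a fixed constant in the loss term without volume, which S9 does not propose. It uses the half-life to argue that early loss is small, and a freely fitted loss coefficient simply absorbs V.
- **A separate error in that the loss term lacks plasma volume.** This is the same unit error. With time⁻¹ the appearance term lacks V equally; with ml/time neither term needs it.
- **That Primary Aim 1 fails because it requires absolute rates.** S2's objective does speak of quantifying rates, but S4 and S10 define Primary Aim 1 as feasibility, including settling the infusion dose, rate and duration.

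**Conclusion.** Wrong as written. The equation behind the substudy's primary outcome balances with neither unit given for the conversion coefficient, and the slope method labels a tracer-dependent rate as a coefficient. The dimensional result needs no assumption beyond S9's own definitions.

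The consequence is conditional. If the undivided slope is what is analysed, the outcome is proportional to labelled LNA concentration. Variation in that concentration then adds noise, and any imbalance between diets, including one arising from infusion changes after feasibility, would enter the comparison. If the balance equation is fitted, or the slope is divided by C_LNA*, this does not arise. The documents do not show that the diet comparison would be biased, and they give no basis for a percentage. The sample sizes are unaffected.

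**What to change.** Revise S9 and one sentence of S10:

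1. Use one convention for both terms: either keep the equation as printed with both coefficients in ml/time, or give both in time⁻¹ and multiply both right-hand terms by plasma volume.
2. Under the ml/time convention, state that the conversion coefficient is the initial slope of V × C_DHA* divided by C_LNA*. Under the time⁻¹ convention, divide also by V. Say how C_LNA* is summarised over the fitting window.
3. State that the synthesis-secretion rate, in nmol/time, is the coefficient in ml/time multiplied by the measured unesterified unlabelled LNA concentration.
4. In S10, name which of the two is primary for the t-test and make the other supportive.

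The cost is wording and a little analysis work. The measurements are already planned, so no new samples are needed and the sample size stays as it is.

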7.6.2 Randomization and Masking

At completion of the pre-intervention phase, participants will be randomized to 1 of the 3 treatment groups by computer. This process eliminates experimenter bias in group assignment. The computer program uses a random numbers generator and is programmed to ensure appropriate numbers of subjects in each arm of the study within a permuted variable block size of 3-4 patients. The computer program generates a treatment assignment associated with each eligible subject's name and study ID number and documents these in an uneditable form with a date stamp. The research dietitian will have password-protected access to the computer-generated treatment assignments. The dietitian will use this information to assign each participant to one of the 3 treatment arms, which will be designated by a letter and color (e.g. Diet A: Orange). Because the 3 diets differ only in the fatty acid content of added visible oils, which are clear and can be distinguished only by nutritional analysis, the participants will remain blinded to their treatment. The research dietitian, by necessity, needs to know which group the patient is assigned in order to provide appropriate foods. No other research or clinical investigators will be told which arm the participants have been assigned.

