7.6.3 Specimen collection for biomarker testing

Blood Collection

To assess the blood compositions of omega-6 and omega-3 fatty acids and their metabolic derivatives, fasting venous blood will be collected at 4 timepoints in the main study (Baseline Visit 3; Diet Phase Visits 1, 2 and 3). Blood will be collected from participants in the optional continuation phase at 6 additional time points (see Table 5: Continuation Phase Visits). Blood will be immediately processed and stored at -80 degrees C. See Table in Appendix 2 for a list of fatty acids and their metabolic mediators that will be assessed.

Genotyping

This project will collect DNA samples from the saliva of well phenotyped overweight subjects for genotyping. Genotyping will be performed on all study participants. Single gene mutations/polymorphisms of interest include: 1) those involved in fatty acid metabolism; 2) those implicated in the pathogenesis of obesity; 3) those implicated in the pathogenesis of medical and psychiatric conditions associated with obesity; 4) those linked to certain behavioral characteristics relevant to obesity and obesity-related comorbidities. On the consent form, participants can designate whether or not the DNA samples can also be stored for future research projects.

Muscle and adipose tissue biopsies and tissue procurement and post-biopsy pain assessment

Fat and muscle biopsies will be obtained before and after the dietary interventions, by the study physicians and/or nurse practitioner. In accordance with established NIDDK practices, biopsies will be performed on the Metabolic Unit or the adjacent 5SW day hospital, as described below.

Subcutaneous adipose tissue (3-5 g) will be removed from the abdominal region by aspiration with a 16-gauge needle under local anesthesia (e.g. 2% xylocaine).

Muscle biopsies (100-250 mg) will be obtained under local anesthesia from the vastus lateralis, as follows. The patient will be prepped and draped in sterile fashion. The muscle biopsy procedure involves numbing a nickel-sized portion of the skin of the thigh with a local anesthetic and making a small incision, approximately 1/4 inch. The biopsy needle is then inserted via the incision through adipose tissue and muscle fascia into the muscle. A small sample of muscle tissue is removed. The incision will then be closed with steri-strips and covered with a dressing. If the muscle is too deep to be reach, the muscle biopsy will not be attempted.

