S4. Study Objectives and Hypotheses (d5-LNA Infusion Amendment)

Study objectives

To demonstrate feasibility for characterizing the hepatic synthesis-secretion rates of DHA and other omega-3 HUFA from infused d5-LNA in humans. To evaluate the effects of lowering the dietary nutrient LA via controlled replacement with OA on DHA synthesis-secretion rates.

Specific hypotheses

Primary aims

To demonstrate feasibility for characterizing the human hepatic synthesis-secretion rates of DHA using a d5-LNA infusion methodology adapted from an NIH rodent model.

To assess increases in hepatic synthesis-rates for DHA from d5-LNA in response to controlled lowering of dietary omega-6 LA from 8 en% to 1 en%.

Primary hypotheses

Hepatic synthesis-secretion rates for DHA from infused d5-LNA can be successfully quantified in humans.

Lowering dietary intake of LA as a controlled variable from 8 en% to 1 en% will significantly increase synthesis-secretion rates for DHA and other omega-3 LCPUFAs.

S5. Subjects

Description of study population

Only participants that are currently enrolled in the main protocol 11-AA-0028, and nearing completion of 12-week intervention phase will be invited to participate in the Infusion Substudy. In order to enroll in the Infusion Substudy, subjects must continue to meet all eligibility criteria for the main protocol in order to enroll (see inclusion and exclusion criteria in Section 6 (pages 12-13) and Appendix 7).

S6. Study Design and Methods – Infusion Substudy

Recruitment

Participants who were randomized to either diet 'A' or diet 'B' and are in their final two weeks of the 12-week diet phase will be invited to participate in the Infusion Substudy. The study dietitian, the only investigator who is unblinded to treatment allocation, will do an initial screen of participant in diet 'A' or diet 'B' who may be eligible to participate. However, enrollment in the Infusion Substudy will require a new informed consent administered by the physicians and/or nurse practitioner specified in Section S11 (page 49).

Overview of Infusion Substudy Design and Methods

After at least 10 consecutive weeks of exposure to study diets, participants randomized to diet 'A' or diet 'B' (Table 7, Figure 8) will be invited to participate in the d5-LNA Infusion Substudy. No matching procedure will be employed. A maximum of 12 subjects in each group will participate.

Table 7: Fatty Acids of 2 Study Diets in the Infusion Amendment

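### Infusion Substudy, Primary Aim 2: the t-test leaves out FADS genotype, which is already collected, and at most 24 women cannot rule genotype out as a confounder

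*Combined protocol and SAP*

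**What the plan says.** Under Primary Aim 2 in S10, the rate for labelled DHA "will be compared in the two diet groups using a t-test" at the 0.05 level. The sample-size text that follows repeats the t-test. Neither place names a covariate.

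The next paragraph of S10 says that genotype, measured in the main protocol, will allow the team to assess whether the low-converter genotype acts as a modifier, "or to rule it out as a confounder". It gives no variant, coding, model, test, decision rule or power for this.

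Other sections supply the context:

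- **S3** says the FADS locus codes for the rate-limiting conversion of LNA to EPA and DHA. It contrasts substantial conversion with minimal conversion by allele.
- **Section 7.6.3**: "Genotyping will be performed on all study participants".
- **S6**: "No matching procedure will be employed" and "A maximum of 12 subjects in each group will participate". Women are invited in their last two weeks on diet, and "enrollment in the Infusion Substudy will require a new informed consent". There is one infusion visit, so no pre-diet rate exists.
- **Section 7.6.2** allocates diets "within a permuted variable block size of 3-4 patients" and names no stratification factor.

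**The concern.** By the protocol's own account, FADS genotype should move the outcome a good deal. It is fixed before randomisation and already in hand. Leaving it out of the model keeps its variance in the error term. It also leaves the one reported difference sensitive to how many slow converters happen to fall in each group.

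The ruling-out clause is a separate problem. The distortion from a prognostic factor is its imbalance between groups multiplied by its effect on the outcome. With 12 per group both are estimated poorly, so a null finding on either excludes little. A reader could still take the clause to mean that the question has been settled.

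**Working it through.** **1. The plan's own figure.** Inputs from Fig. 10: means 14.1 and 23.547 (difference 9.447), SDs 7.762, 6.4684 and 3.7647, alpha 0.05, power goal 0.80. The critical t of 2.0739 on 22 df shows a two-sided test. With exact noncentral-t power the required sizes are 12, 9 and 4 per group, with power 0.8130, 0.8284 and 0.8386. All agree with Fig. 10. These sizes cover only the diet contrast.

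**2. Chance imbalance.** Take the number of low converters in each group as independent Binomial(12, p). The frequency p is not in the documents, so a range is shown.

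| p (assumed) | P(groups differ by 3 or more) |
|---|---|
| 10% | 8% |
| 25% | 24% |
| 50% | 31% |

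If the genotype effect were as large as the planned diet effect (assumption), an imbalance of 3 in 12 would shift the unadjusted difference by 3/12 × 9.447 = 2.36, a quarter of the planned difference.

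**3. Could a balance check rule this out?** S10 specifies no check, so this is an illustration. At 12 v 12, Fisher's test reaches p < 0.05 only from splits such as 0 v 5, 1 v 7 or 3 v 9. Among imbalances of three or more, it does so in about 6-7% of cases at p = 25-50%.

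**4. Is the t-test valid?** Simulate 12 v 12 with no diet effect, a genotype effect of 9.447, a within-genotype SD of 5 (assumed) and 25% or 50% low converters. The unadjusted t-test rejects in about 5% of runs. Its error rate holds.

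**5. What adjustment gains.** Take SD 7.762 and 12 per group, with genotype explaining a share R² of the variance (assumed). Then SE = 7.762 × √(1 − R²) × √(2/12) on 21 df. The lower figure in each range below multiplies the variance by about 1 + 1/20, to allow for chance correlation between genotype and diet.

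| R² | SE before that allowance | Power |
|---|---|---|
| Unadjusted, 22 df | 3.17 | 81.3% |
| 0 | 3.17 | 79-81% |
| 10% | 3.01 | 83-85% |
| 20% | 2.83 | 87-89% |
| 30% | 2.65 | 91-92% |

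**6. Effect modification, a separate question.** With k low converters among the 12 in each group, the interaction has SE = SD × √(2/k + 2/(12 − k)) on 20 df. For k = 3 and SD 7.762, SE = 7.762 × √(2/3 + 2/9) = 7.32. The ranges run from k = 3 (25%) to k = 6 (50%).

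| SD | Power, interaction 9.447 | Power, half that size | 95% CI half-width |
|---|---|---|---|
| 7.762 | 23-30% | 9-11% | 13.2-15.3 |
| 6.4684 | 31-40% | 11-14% | 11.0-12.7 |
| 3.7647 | 72-83% | 24-31% | 6.4-7.4 |

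Only the smallest SD, with about half the women low converters, reaches 80%, and then only for an interaction as large as the whole diet effect.

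**The case against.** The strongest reply is that diet is randomised. Chance imbalance in any covariate is already covered by the error rate of the t-test and by its SD, so adjustment is an improvement and not the repair of a fault. This stands, and step 4 confirms it. A reader might infer that the planned test is biased or invalid. The documents do not support that. The only reservation is that women enter after randomisation, by reaching the last two weeks and consenting again. That is a general concern; nothing in the documents links consent to genotype, and adjusting for genotype would not cure selection.

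Four other inferences should also be resisted:

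- **Interaction power is not evidence about confounding.** Step 6 bears on the modifier half of the sentence only. It must be read at all three SDs: 7.762 is 33% of the larger mean and 55% of the smaller, above the 20-30% that S10 states, so that row alone would be too pessimistic.
- **Genotype cannot be called the best available baseline predictor.** Fasting blood fatty acids are also measured at Baseline Visit 3 (section 7.6.3), and nothing ranks one above the other.
- **It cannot be said that a null check would be presented as reassurance.** The plan defines neither a check nor a reporting rule.
- **It cannot be said that no genotype analysis is intended.** S3 and S10 both announce one. It is unspecified.

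It is also fair to say that this is a small substudy whose first aim is feasibility. That limits the weight of the point. It does not make the ruling-out claim attainable.

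**Conclusion.** The point holds as a matter of precision and of an unsupportable claim. The sample size is right for the diet contrast, and the t-test keeps its 5% level. But the planned comparison ignores a baseline factor that the protocol describes as governing the conversion being measured, and it promises a conclusion about confounding that at most 24 women cannot give.

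The sizes rest on assumptions. The imbalance probabilities depend on a low-converter frequency that the documents do not state and on a simple low/not-low split. The power gain depends on how much variance genotype explains, also not stated. S10 also uses the first four infusions to set dose, rate and duration, and does not say whether those women count in the diet comparison. If they do not, fewer than 12 per group could be available and precision would be lower than shown.

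**What to change.** In S10, Primary Aim 2:

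1. Make the primary analysis a linear model of the DHA synthesis-secretion rate on diet group plus one FADS variant named in advance, coded as allele count. Report the adjusted difference with its 95% CI.
2. Keep the unadjusted t-test as a sensitivity analysis.
3. Delete the clause about ruling genotype out as a confounder, and tabulate genotype by diet group instead.
4. Report the genotype-by-diet interaction only as an exploratory estimate with its 95% CI.

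The cost is wording plus one of 22 degrees of freedom. No new data or procedure is needed. The downside is a loss of up to about two points of power if genotype explains nothing. Naming the variant and its coding beforehand also prevents either from being chosen after the results are seen.

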We will use a t-test to compare the synthesis-secretion rates and coefficients measured at 4 weeks in the two groups (A and B). Assuming a 20-30% standard deviation in the synthesis-secretion rates based on our prior kinetic work in humans (74) and rodents (64) and a 67% difference in expected change in kinetics consistent with Pawlosky et al (74) and prior measured changes in DHA concentrations, we calculated required sample size(s) (Fig. 10). To detect these effect sizes, at a power of 80% and an alpha of 0.05, we will need 4-12 individuals per group.

Fig. 10. Sample Sizes for Endogenous DHA Synthesis Amendment

Sample Size Calculation (Spreadsheet1)	
Two Means, t-Test, Ind. Samples	
H0: Mu1 = Mu2	
Population Mean Mu1	14.1000
Population Mean Mu2	23.5470
Population S.D. (Sigma)	7.7620
Standardized Effect (Es)	-1.2171
Type I Error Rate (Alpha)	0.0500
Critical Value of t	2.0739
Power Goal	0.8000
Actual Power for Required N	0.8130
Required N (per group)	12.0000

Sample Size Calculation (Spreadsheet1)	
Two Means, t-Test, Ind. Samples	
H0: Mu1 = Mu2	
Population Mean Mu1	14.1000
Population Mean Mu2	23.5470
Population S.D. (Sigma)	6.4684
Standardized Effect (Es)	-1.4605
Type I Error Rate (Alpha)	0.0500
Critical Value of t	2.1199
Power Goal	0.8000
Actual Power for Required N	0.8284
Required N (per group)	9.0000

Sample Size Calculation (Spreadsheet1) Two Means, t-Test, Ind. Samples H0: Mu1 = Mu2	
	Value
Population Mean Mu1	14.1000
Population Mean Mu2	23.5470
Population S.D. (Sigma)	3.7647
Standardized Effect (Es)	-2.5094
Type I Error Rate (Alpha)	0.0500
Critical Value of t	2.4469
Power Goal	0.8000
Actual Power for Required N	0.8386
Required N (per group)	4.0000

S11. Human Subjects protection – Infusion Substudy

For human subjects protection issues that apply to both the main protocol and the Infusion Substudy, please see Section 12 (Page 38) of the main protocol. Additional issues that apply to the Infusion Substudy are addressed in the following sections.

Justification of sensitive procedures

Procedures that may cause some discomfort to subjects:

Prolonged fast for d5-LNA Infusion: Participants are required to fast for up to 16 continuous hours. Participants will be provided with IV fluids but are likely to experience some hunger during the 8-hour infusion. They will be provided with a meal immediately after infusion.

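### Infusion Substudy: the 4-12 per group does not follow from the stated 20-30% SD, because two of the three SDs in Fig. 10 come from a different base

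*Combined protocol and SAP*

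**What the plan says.** In S10 (Estimation of Power and Sample Size), the substudy plans a t-test of DHA synthesis-secretion rates between diets A and B. The variability is introduced as "Assuming a 20-30% standard deviation in the synthesis-secretion rates", attributed to earlier kinetic work in humans and rodents. The effect is "a 67% difference in expected change in kinetics". At 80% power and alpha 0.05 the text concludes that "we will need 4-12 individuals per group". The preceding subsection of S10 gives the same range.

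Fig. 10 shows three sample-size panels. All use "Population Mean Mu1 14.1000" and "Population Mean Mu2 23.5470". The first has "Population S.D. (Sigma) 7.7620" and requires 12 per group. The second has "Population S.D. (Sigma) 6.4684" and requires 9. The third has an SD of 3.7647 and requires 4. The text does not say which mean the 20-30% refers to.

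S6 caps each group at 12, and S2 caps the substudy at 24 women.

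**The concern.** The text and the figure it cites should describe the same calculation. The figure's range of 4 to 12 is carried into the text, but the SDs behind it are not the SDs the text states. A reader therefore cannot tell what variability the maximum of 12 per group is meant to cover.

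This matters because 12 per group is also the recruitment cap. It sets how many women may undergo an 8-hour infusion, two intravenous lines and a 16-hour fast, which S13 classes as more than minimal risk without direct benefit. Anyone weighing that exposure is told that the number rests on a 20-30% SD.

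**Working it through.** **Inputs (S10, Fig. 10).** Means 14.1 and 23.547; difference 9.447; ratio 23.547 / 14.1 = 1.67, which is the stated 67%. SDs 7.7620, 6.4684 and 3.7647. Alpha 0.05, two-sided (not written, but implied by the printed critical t of 2.0739 on 22 df). Power goal 0.80.

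**Step 1: reproduce Fig. 10.** Method: exact two-sample t-test with d = 9.447 / SD, df = 2n - 2 and noncentrality d × √(n/2); n is the smallest value with power of at least 0.80.

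| SD | d | n per group | Power | Fig. 10 |
|---|---|---|---|---|
| 7.7620 | 1.217 | 12 | 0.813 | 12; 0.8130 |
| 6.4684 | 1.460 | 9 | 0.828 | 9; 0.8284 |
| 3.7647 | 2.509 | 4 | 0.839 | 4; 0.8386 |

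The panels are internally correct and were read correctly from the PDF. What needs explaining is the choice of SDs.

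**Step 2: express each SD as a percentage.** The average mean is (14.1 + 23.547) / 2 = 18.8235.

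| SD | % of 14.1 | % of 18.8235 | % of 23.547 |
|---|---|---|---|
| 3.7647 | 27 | 20 | 16 |
| 6.4684 | 46 | 34 | 27 |
| 7.7620 | 55 | 41 | 33 |

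On the lower and average means only the smallest SD falls within 20-30%. On the higher mean only the middle one does. The largest exceeds 30% in every column.

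**Step 3: required n from the stated SD.** Same method.

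| Base | n at 20% | n at 25% | n at 30% |
|---|---|---|---|
| Lower mean, 14.1 | 3 | 4 | 5 |
| Average, 18.8235 | 4 | 6 | 7 |
| Higher mean, 23.547 | 6 | 8 | 10 |

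No row gives 4-12, and none reaches 12.

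**Step 4: a possible origin.** 14.1 + 23.547 / 2 = 25.8735. Then 0.30 × 25.8735 = 7.76205 and 0.25 × 25.8735 = 6.46838, which are the two larger SDs to the printed precision. The smallest is 0.20 × 18.8235 = 3.7647. The pattern fits a correctly averaged mean in the 20% case and a dropped bracket in the 25% and 30% cases.

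**Step 5: direction.** At 12 per group, power is 0.975 for an SD of 30% of the average mean (5.647) and 0.813 for SD 7.762.

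**Step 6: ten per group.** S10 uses the first four infusions to set dose, rate and duration. If those four were left out, two from each group, 10 per group would remain within the cap of 24.

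| SD | What it is | Power at 10 per group |
|---|---|---|
| 4.230 | 30% of lower mean | 0.997 |
| 5.647 | 30% of average mean | 0.942 |
| 7.064 | 30% of higher mean | 0.807 |
| 7.762 | SD behind n = 12 | 0.730 |

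**The case against.** The strongest reply is that nothing is lost. The cap of 12 per group is larger than the stated assumption needs on any base, so the planned maximum is conservative. That stands, and it limits the point to one of reporting. It does not make the stated range follow from the stated assumption.

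A second reply is that the text names no denominator, so the 20-30% may refer to something else. This is fair as to which percentages to quote. The average mean is an assumption, supported by its making the smallest SD exactly 20%. But neither group mean nor their average reconciles text and figure.

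A reader might infer that the substudy is underpowered, at about 73%. The documents do not support that. The figure needs three conditions together: an SD of 7.762, which lies outside the stated range on every base; exclusion of the first four infusions, which the plan nowhere states; and an even split of those four. The outcome in S9 is a coefficient per unit of plasma LNA concentration under assumed linearity, so a changed infusion rate need not prevent pooling. At an SD within the stated range, 10 per group still gives at least 80%.

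A reader might also infer that the figure is right and that the text should simply say 20-41%. The documents do not establish this either. The text ties 20-30% to prior kinetic work, nothing in the documents supports 41%, and the match in Step 4 points to the SDs as the likelier slip.

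**Conclusion.** The point holds as an internal contradiction in S10. The stated 20-30% SD gives 4-7 per group on the average mean (3-5 on the lower, 6-10 on the higher), whereas the 4-12 reported comes from SDs of 20%, 34% and 41% of the average mean. That the figure does not follow from the text does not depend on which of these bases is used; the particular percentages do. The missing bracket is inferred from an exact numerical match and is not stated anywhere.

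The consequence is small. At the cap of 12 per group the error is on the safe side: about 97% power at 30% of the average mean, and 81% at the largest SD entered. Power falls to about 73% only under the combined conditions set out above, so 73% should not be quoted as the power of the plan.

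**What to change.** Name the mean to which the SD percentage refers, then reconcile the text with Fig. 10 in one of two ways:

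- If the two larger SDs are a slip, correct them to 25% and 30% of the average mean (4.7059 and 5.6471) and restate the requirement as 4-7 per group: 4, 6 and 7 at 20%, 25% and 30%.
- If the larger SDs were intended, restate the assumption as 20-41% of the average mean and give the evidence for the upper figure.

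In either case, state the power that the maximum of 12 per group gives under the chosen SD. If the larger SD is kept, also say whether the first four infusions enter the comparison, and give the power of about 73% if they do not (10 per group).

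The cost is a few sentences and, under the first option, two recalculated panels. No additional women are needed. Under the first option the required number is smaller than the present cap, so the sponsor should say why up to 12 per group would still be infused.
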